# **Evaluation Post-Unblinding & Permanent Discontinuation**

Following unblinding, patients who have not yet met the primary study endpoint (death), and are currently on protocol therapy (active arm) may receive BBI608 on study based on the clinical judgement of the investigator and local REB approval that this is in the patients' best interest, providing the patient is fully informed and provides consent, if this agent is not a nationally licenced medicinal product and/or are not funded by the normal health care infrastructure. Please refer to sections 9.1.1 and 9.2.1.

	At 4 weeks (28 days) post-	Every 8 weeks (56 days) thereafter (until deterioration to ECOG PS 4 or				
Required Investigations	protocol treatment 	hospitalization for end of life care)				
History & Physical						
History & Physical Exam	X					
ECOG PS	X					
Weight	X					
Vital signs	X					
Hematology						
CBC + differential	X					
Platelet count	X					
Biochemistry						
Creatinine, Total Bilirubin, ALT, Alkaline Phosphatase, LDH, Albumin, Potassium, Magnesium, Phosphate	X					
Urinalysis	X					
Cardiology Assessment						
ECG	X	As clinically indicated				
Radiology & Imaging 						
CT/MRI scan (as per baseline assessment)		No longer required for patients who did not have objective disease progression prior to unblinding. But please report disease assessment data in EDC if done.				
Correlative Studies & Tissue Banking						
Submission of representative block of diagnostic tumour tissue to central bank 		See table above				
Blood, plasma, serum, RBC pellet, buffy coat		See table above				
Adverse Events						
Adverse Event assessment for ongoing and related to BBI608 4.5		X				
New Anti-cancer Therapy						
Reporting of new anti-cancer therapy		X				
Overall Survival						
Assess for survival of patient		X 				
1 D-tit	1.11 . 1 . 1.					

- 1 Patients are to be assessed every 4 weeks (28 days) while on study medication and until the first regularly scheduled 4 week assessment at which the patient has been off study therapy for a minimum of 28 days.
- 2 Tumour measurement and evaluation by RECIST 1.1 criteria. The same method of assessment and the same technique should be used to identify and report each lesion at baseline and at reassessment during treatment. Tumour evaluations will continue until progressive disease is documented (as described in section 10). For patients who remain on protocol therapy after objective disease progression has been documented, no further imaging assessments are mandated, but where these occur as a component of care, tumour measurements and assessment must be reported.
- 3 On request by the central tumour bank
- 4 Adverse events will be recorded and graded according to the NCI Common Terminology Criteria for Adverse Events (see Appendix V).
- 5 Adverse event assessment by phone will be performed at 24-48 hours after start of protocol treatment, and at 2 and 6 weeks (i.e. approximately days 14 and 42, respectively)after randomization to assess for tolerability of dosing regimen.
- In the event that the patient is unable to attend clinic, post-progression follow-up may be by means of telephone contact.

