#### 7.3 Registration/Randomization

Patients will be randomized 1:1 between the two treatment arms and the randomization will be provided electronically.

AMEND #2: 2014-FEB-24

Note: The validity of results of the trial depends on the authenticity of, and the follow-up of, all patients entered into the trial. Under no circumstances, therefore, may an allocated patient's data be withdrawn prior to final analysis, unless the participant withdraws from the trial and requests that data collection/submission cease from the point in time of withdrawal.

All eligible patients admitted to the trial will be followed by the coordinating center. It is the responsibility of the physician in charge to satisfy himself or herself that the patient is indeed eligible before requesting randomization.

All randomized patients are to be followed until death or until sites are informed by NCIC CTG that further follow-up is no longer required. The follow-up requirements for ineligible patients who have received no protocol therapy include submission of the Baseline Report plus an annual minimal follow-up form. Data submission for ineligible participants who have received at least one dose of protocol therapy should be followed according to the protocol to allow for treatment and adverse event assessment.

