#### 9.0 EVALUATION DURING AND AFTER PROTOCOL TREATMENT

All patients entered on study must be evaluated according to the schedule outlined in Appendix I with documentation submitted according to the schedule in Appendix IV.

Evaluations will be performed at different intervals throughout the study. If dose delays occur for any reason on the study, other study assessments, including assessment by physician and Quality of Life questionnaires, will not be delayed, but should continue at the time indicated from randomization.

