#### 9.2 Evaluation After Protocol Treatment Discontinuation

Investigations		Timing from Randomization	
Physical Examination	
 
Physical examination
 
Vital signs
 
Weight + ECOG Performance status
 
	Every 4 weeks (every 28 days) after randomization until the first regularly scheduled 4 week	
Economics	Resource Utilization Assessment	assessment at which the patient has been off study therapy for a minimum of 28 days, and every 8	
Adverse Events 	* Adverse Event evaluation must be done at each study visit for the preceding reporting period 	weeks (56 days) thereafter until deterioration to ECOG PS 4 or hospitalization for end of life care.	
Overall Survival	• Assess for survival of patient 	Every 4 weeks (every 28 days) after randomization until the first regularly scheduled 4 week assessment at which the patient has been off study therapy for a minimum of 28 days, and every 8 weeks (56 days) thereafter.	
Other	• Serum or urine pregnancy test 		
Investigations	Serum CEA		
Hematology	CBC + differential, Platelet count	Every 4 weeks (every 28 days) after randomization	
Biochemistry	Creatinine, Total Bilirubin, ALT,     Alkaline Phosphatase, LDH, Albumin,     Potassium, Magnesium, Phosphate	until the first regularly scheduled 4 week assessment at which the patient has been off stud therapy for a minimum of 28 days	
Urinalysis	Dipstick (including protein, specific gravity, glucose and blood)		
Cardiology Assessment	• ECG	At the first regularly scheduled 4 week assessment at which the patient has been off study therapy for a minimum of 28 days	
Radiology & Imaging	• CT/MRI scan as per baseline assessment with tumour measurement and evaluation by RECIST 1.1 criteria 	Every 8 weeks (56 days) after randomization until objective disease progression is documented 	
Correlative Studies & Tissue Banking	• Submission of whole blood sample to central tumour bank 	At 4, 8 and 12 weeks after randomization 	
Quality of Life	• EORTC QLQ-C30 	At 4, 8, 12, 16 and 24 weeks after randomization or	
Health Utilities	• Health Utilities Index (HUI3) 6	until deterioration to ECOG PS 4 or hospitalization for end of life care 	

 Adverse events will be recorded and graded according to the NCI Common Terminology Criteria for Adverse Events (see Appendix V).

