 In the event that patient is unable to attend clinic, post-progression follow-up may be by means of telephone contact.

 In women of childbearing potential only. The minimum sensitivity of the pregnancy test must be 25 IU/L or equivalent units of HCG.

 The same method of assessment and the same technique should be used to identify and report each lesion at baseline and at reassessment during treatment. Tumour evaluations will continue until progressive disease is documented (as described in section 10).

 Details for collection, processing, storing and shipping these samples will be provided in a separate procedure manual.

 To be completed in clinic.

AMEND #3: 2014-OCT-01

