# APPENDIX I - PATIENT EVALUATION FLOW SHEET

Required Investigations	Pre-study (i.e., Pre- treatment)	2 hours after the first dose of BBI608, then as clinically indicated	Every 4 weeks/ 28 days 	Every 8 weeks/ 56 days	At 4 weeks (day 28),8 weeks (day 56), &12 weeks (day 84)	At 4 weeks (day 28),8 weeks (day 56),12 weeks (day 84), 16 weeks (day 112) & 24 weeks (day 168)	At 4 weeks (28 days) post- protocol treatment 	At 4 weeks (28 days) post- protocol treatment, & every 8 weeks (56 days) thereafter (until deterioration to ECOG PS 4 or hospitalization for end of life care)
History & Physical	treatment)	mareacea	20 days	uujs	(day 01)	100)	a causioni	ond of me care)
History & Physical Exam	$\mathbf{X}^2$		X					X
ECOG PS	X		X					X
Weight	X		X					X
Height	X							
Vital signs	X		X					X
Hematology 								
CBC + differential	X		X				X	
Platelet count	X		X				X	
Biochemistry 								
Creatinine  , Total Bilirubin, ALT, Alkaline Phosphatase, LDH, Albumin, Potassium, Magnesium, Phosphate	X		X				X	
Urinalysis	X		X				X	
Economics								
Resource Utilization Assessment			X					X
Cardiology Assessment								
ECG	X	X					X	
Radiology & Imaging 								
CT/MRI scan (as per baseline assessment)	X			$X^6$				
Correlative Studies & Tissue Banking								
Submission of representative block of diagnostic tumour tissue to central bank 								
Blood, plasma, serum, RBC pellet, buffy coat	X				X			
Pharmacokinetics								
Blood collection for sparse PK analysis					$X^8$			

continued on next page ...

Amendment #1: 2013-JUN-12

Required Investigations	Pre-study (i.e., Pre- treatment)	2 hours after the first dose of BBI608, then as clinically indicated	Every 4 weeks/ 28 days 	Every 8 weeks/ 56 days	At 4 weeks (day 28),8 weeks (day 56), &12 weeks (day 84)	At 4 weeks (day 28),8 weeks (day 56),12 weeks (day 84), 16 weeks (day 112) & 24 weeks (day 168)	At 4 weeks (28 days) post- protocol treatment 	At 4 weeks (28 days) post- protocol treatment, & every 8 weeks (56 days) thereafter (until deterioration to ECOG PS 4 or hospitalization for end of life care)
Other Investigations	T							
Pregnancy test, serum or urine (if applicable) 	X		$X^{10}$				$X^{10}$	
Serum CEA	X		X				X	
Adverse Events								
Adverse Event assessment 11. 12	X		X					X
Quality of Life								
EORTC QLQ-C30	X					$X^{13}$		
Health Utilities								

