Health Utilities Index (HUI3)	X					$X^{13}$		
Overall Survival								
Assess for survival of patient			X					$X^{14}$

- Patients are to be assessed every 4 weeks (28 days) while on study medication and until the first regularly scheduled 4 week assessment at which the patient has been off study therapy for a minimum of 28 days.
- 2 Medical history must include date of diagnosis including histological documentation of malignancy, documentation of *K-ras* status of tumour, prior anticancer therapy and prior date(s) of disease progression. Note: Documentation of progression, as described in section 10.2, or intolerance, as described in sections 5.1.4, 5.1.5 and/or 5.1.6, must be submitted.
- 3 Bloodwork Timing: Pre-treatment blood draws may be done up to 14 days prior to randomization. Every effort should be made to do interim blood draws within 24 hours of the day specified in the protocol.
- 4 Baseline creatinine or creatinine clearance may be used to demonstrate eligibility as per section 5.1.17
- Tumour measurement and evaluation by RECIST 1.1 criteria. The same method of assessment and the same technique should be used to identify and report each lesion at baseline and at reassessment during treatment. Tumour evaluations will continue until progressive disease is documented (as described in section 10). For patients who remain on protocol therapy after objective disease progression has been documented, no further imaging assessments are mandated, but where these occur as a component of care, tumour measurements and assessment must be reported.
- MPORTANT NOTE: For the first 96 patients, for the first 8-week scan, disease assessment MUST be entered into EDC expeditiously, due to the early stopping rule (DCR at first response assessment to project whether continued treatment with BBI608 would be futile) see section 14.5
- 7 On request by the central tumour bank
- 8 Please refer to the specific Sparse PK sampling laboratory manual for full details about blood collection, storage, and shipment
- 9 In women of childbearing potential only. The minimum sensitivity of the pregnancy test must be 25 IU/L or equivalent units of HCG.
- 10 In women of childbearing potential only a negative pregnancy test must be demonstrated every 4 weeks until 4 weeks after the administration of the final dose of protocol therapy.
- 11 Adverse events will be recorded and graded according to the NCI Common Terminology Criteria for Adverse Events (see Appendix V).

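### Both Appendix I flow sheets end long-term survival assessment at ECOG PS 4 or end-of-life admission, contradicting sections 7.3, 9.2 and 9.2.1 on how the primary endpoint is ascertained

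*Protocol*

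**What the plan says.** Section 9.0 makes the flow sheet binding: "All patients entered on study must be evaluated according to the schedule outlined in Appendix I". The same sentence sends documentation to the Appendix IV schedule.

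The main Appendix I sheet has a row "Assess for survival of patient" with two marks.
- One is in the every-4-weeks column. Footnote 1 limits that column: "Patients are to be assessed every 4 weeks (28 days) while on study medication and until the first regularly scheduled 4 week assessment". The visit meant is the first one that falls 28 days or more after treatment stops.
- The other is in the last column, which covers the 4-week post-treatment visit and then runs "every 8 weeks (56 days) thereafter (until deterioration to ECOG PS 4 or hospitalization for end of life care".

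The post-unblinding sheet added by Amendment 3 has a single survival mark. It sits in the column headed "Every 8 weeks (56 days) thereafter (until deterioration to ECOG PS 4 or", and the heading continues with end-of-life hospitalization. The footnotes to both marks permit telephone contact for patients who cannot attend, but do not lift the limit.

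The body of the protocol differs. Section 9.2 applies the PS 4/end-of-life stop to physical examination, resource use and adverse events, then gives survival a separate row that ends simply with "off study therapy for a minimum of 28 days, and every 8 weeks (56 days) thereafter". Section 9.2.1 repeats the uncapped survival schedule for the post-unblinding period. Section 7.3 states: "All randomized patients are to be followed until death or until sites are informed by NCIC CTG" that no more follow-up is needed.

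Sections 10.1.2 and 14.2 censor patients who are alive or lost to follow-up at the last date they were known to be alive. Section 14.5 sets the final analysis at 195 events in the 217 ITT-March patients.

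**The concern.** Two instructions that both bind the site give different stopping rules for collecting the primary endpoint. A coordinator who works from the flow sheet, as section 9.0 directs, has no scheduled survival contact after the patient reaches PS 4 or enters end-of-life care. That is the point at which death is most likely to follow soon.

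If the death is then not learned of, the patient is censored shortly before it. Such censoring depends on prognosis. It breaks the independence that the Kaplan-Meier estimate and the log-rank test rely on, pushes estimated survival upward, and removes events. Because the final analysis is triggered by a count of deaths close to the whole population, a modest number of unrecorded deaths could also prevent the trigger from being reached.

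**Working it through.** **1. The schedules side by side**

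| Source | Survival after stopping treatment | Stops at PS 4 / end-of-life admission? |
|---|---|---|
| Section 7.3 | Until death or release by the coordinating group | No |
| Section 9.2 | Every 4 weeks to the first visit at least 28 days off therapy, then every 8 weeks | No (other rows: yes) |
| Section 9.2.1 | Same | No |
| Appendix I, main sheet | 4-week post-treatment visit, then every 8 weeks | Yes |
| Appendix I, post-unblinding sheet | Every 8 weeks | Yes |

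The every-4-weeks mark in the main sheet does not rescue it. That column closes at the first scheduled visit at least 28 days off therapy, so later survival contact rests on the capped column alone. Section 9.2 puts the cap on its neighbouring rows and leaves it off survival, so the cap appears not to have been meant for survival.

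**2. The plan's own figures**

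Inputs from section 14.5: 195 events, 217 patients, HR 0.70 or 0.77, two-sided 0.05. Allocation is 1:1.

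- Trigger: 195/217 = 89.9%, matching the stated 90%.
- Power = Φ(√d/2 × |ln HR| − 1.96).
- HR 0.70: √195/2 × 0.3567 − 1.96 = 0.530, power 70.2% (stated 70%).
- HR 0.77: √195/2 × 0.2614 − 1.96 = −0.135, power 44.6% (stated 43%; another standard approximation gives 44.2%).

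The stated figures reproduce to within 2 points and are not in question.

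**3. Slack in the trigger**

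217 − 195 = 22 patients, and 22/217 = 10.1%. With 23 unrecorded deaths the most that can ever be counted is 194. The 22 is an upper limit on tolerable loss, because patients still alive or withdrawn draw on the same allowance.

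**4. Sensitivity to the share of deaths never recorded**

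The protocol gives no such share; f is assumed. Observable deaths = 217 × (1 − f). The power columns use no more than 195 deaths and assume an undistorted hazard ratio.

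| f | Deaths observable | 195 reachable? | Power, HR 0.70 | Power, HR 0.77 |
|---|---|---|---|---|
| 5% | 206 | yes | 70.2% | 44.6% |
| 10% | 195 | just | 70.2% | 44.6% |
| 15% | 184 | no | 67.8% | 42.7% |
| 20% | 174 | no | 65.2% | 40.6% |
| 30% | 152 | no | 59.4% | 36.3% |

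**5. Direction of the bias**

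Illustrative simulation: one arm of 108 patients, exponential survival with the design control median of 4.6 months, and a share f of patients censored 1 month before death. The estimated median moves from about 4.7 months with no loss to about 5.0 (f = 10%), 5.6 (20%) and 6.4 (30%). The 1-month gap and f are assumptions. The result shows direction, not expected size.

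**The case against.** **The strongest case against.** A lost death requires a site to overlook several other instructions. Section 9.0 binds sites to Appendix IV as much as to Appendix I. Appendix IV asks for a Death Report within 4 weeks of death, with no PS 4 limit, and an 8-weekly Follow-up Report on everyone permanently off treatment. Section 12.4 points to section 9.2 for off-treatment follow-up, and the post-unblinding sheet itself refers the reader to 9.1.1 and 9.2.1. In that sheet the column heading is not applied literally to every row: some cells say to act as clinically indicated or to see the other table.

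**What stands.** These provisions make a large loss less likely, and a death reported through any of them counts as an event. They do not settle which schedule governs survival contact, and a Death Report can be filed only if the site learns of the death.

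**Stronger readings that the protocol does not support**

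- *A reader might infer that nearly half of the required deaths depend on the post-unblinding sheet.* With medians of 4.6 and 6.0 months, exponential survival, and even accrual of 97 patients to January 10, 2014 and 120 more to March 28, about 105 deaths are expected by May 23, 2014, leaving 195 − 105 = 90. But that sheet is dated October 1, 2014. The same model gives about 153 deaths by then, leaving about 42. Earlier deaths fall under the main sheet, which has the same limit.
- *A reader might infer a bias between arms*, because BBI608 continuers stay on the uncapped 4-weekly column. Section 14.5 directed all patients to stop, with BBI608 continued only case by case, and continuers who stop move to the same capped column. Any hazard ratio distortion would rest on arm-specific loss rates that the protocol does not supply.
- *A reader might infer that telephone contact is barred before documented progression.* The footnote says "post-progression follow-up may be by means of telephone contact". That is permissive, and sections 12.1 and 12.4 ask for continued follow-up of patients who no longer attend.

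**Conclusion.** The contradiction is certain. It appears in both flow sheets, conflicts with three sections of the protocol, and concerns ascertainment of the primary endpoint. It should be corrected.

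The consequence is conditional. If sites followed the flow sheet and did not otherwise learn of the deaths, censoring would be informative and would overstate survival. The only threshold that follows from the protocol's own numbers is 22 patients (10.1% of 217): beyond it the 195-death trigger cannot be met. The power and median figures for given loss rates rest on assumed values of f and, for the median, on exponential survival and a 1-month gap. The protocol does not show how many deaths would be lost, and the number may be small. The stated power figures need no change.

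**What to change.** In both Appendix I sheets, take the survival row out of the capped column and give it the schedule already in force elsewhere. Survival would be assessed every 8 weeks after the post-treatment visit, until death or release by the coordinating group, and would not be stopped by PS 4 or end-of-life hospitalization. The cap can stay on the rows to which section 9.2 applies it.

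Before the final database lock, obtain one survival-status update for each patient whose contact stopped at PS 4 or at end-of-life admission.

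Deleting the words that tie the telephone footnotes to progression is optional tidying.

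The cost is a wording change in two tables and one status query per affected patient, with no new visits.

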# APPENDIX II - PERFORMANCE STATUS SCALES/SCORES

# PERFORMANCE STATUS CRITERIA

Karnofsky and Lansky performance scores are intended to be multiples of 10.

ECOG (Zubrod)		Karnofsky			Lansky*		
Score	Description	Score	Description		Description		
0 pre-disease	Fully active, able to carry on all	100	Normal, no complaints, no evidence of disease.		Fully active, normal.		
	pre-disease performance without restriction.	90	Able to carry on normal activity; minor signs or symptoms of disease.	90	Minor restrictions in physically strenuous activity.		
	Restricted in physically strenuous activity but		Normal activity with effort; some signs or symptoms of disease.	80	Active, but tires more quickly.		
ambulatory and able to carry out work of a light or sedentary nature, e.g. light housework, office work.		70	Cares for self, unable to carry on normal activity or do active work.	70	Both greater restriction of and less time spent in play activity.		
selfcare but unable any work activities	Ambulatory and capable of all selfcare but unable to carry out	60	Requires occasional assistance, but is able to care for most of his/her needs.	60	Up and around, but minimal active play; keeps busy with quieter activities.		
	any work activities. Up and about more than 50% of waking hours.	50	Requires considerable assistance and frequent medical care.	50	Gets dressed, but lies around much of the day; no active play; able to participate in all quiet play and activities.		
3	Capable of only limited selfcare; confined to bed or		Disabled, requires special care and assistance.	40	Mostly in bed; participates in quiet activities.		
chair more hours.	chair more than 50% of waking hours.	30	Severely disabled, hospitalization indicated. Death not imminent.	30	In bed; needs assistance even for quiet play.		
4 ca	Completely disabled. Cannot carry on any selfcare. Totally	20	Very sick, hospitalization indicated. Death not imminent.	20	Often sleeping; play entirely limited to very passive activities.		
	confined to bed or chair.	10	Moribund, fatal processes progressing rapidly.	10	No play; does not get out of bed.		
* The conversion of the Lansky to ECOG scales is intended for NCI reporting purposes only.							

Amendment #1: 2013-JUN-12

